#### **4.8. Data and Safety Monitoring Plan**

University of Minnesota Institutional Review Board (IRB) approval will be obtained prior to study initiation. Data and safety monitoring will be conducted by the IRB, the PI, and independently by qualified staff appointed by the CTSI. Monitoring by the CTSI will occur annually at a minimum. The PI will have primary responsibility for recording of events, follow up, and reporting to the IRB.

Any adverse events will be recorded immediately in the source document and in the appropriate study log for reporting to the IRB. The clinical course of any adverse event will be followed until resolution, stabilization, or until it has been determined that study participation is not the cause. Reports of all adverse events (including follow-up information) will be submitted to the IRB according to IRB requirements. Reports of any serious adverse events (defined as any event that is: 1) fatal 2) life threatening 3) requires or prolongs a hospital stay 4) results in persistent or significant disability or incapacity 5) results in a congenital anomaly or birth defect or 6) results in an important medical event) will be submitted to the IRB according to IRB requirements. Reports of any unanticipated problems involving risk to subjects or others (UPIRTSO) will be submitted to the IRB according to IRB requirements.

Subjects may discontinue participation in the study at any time, for any reason. Subjects will be withdrawn from the study in the case of a significant adverse event, consent withdrawal, or failure of the subject to adhere to protocol requirements. Failure to adhere to the protocol will be defined as compliance with <80% of requested study activities. In addition, any subject observed to have unacceptable responses to research procedures or to be unable to safely tolerate participation in the study as judged by the study investigator will be withdrawn.

The study will be stopped if >50% of subjects cannot meet compliance with >80% of study activities. This rule will be implemented after enrollment of the first 6 subjects.

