#### **4.7. Methods of Data Analysis**

The primary outcome will be HgbA1c at the end of the 12-week study period. Results will be compared pre and post diet intervention (within an individual subject) using paired t-tests and between dietary interventions (LoBAG30 versus control) using unpaired t-tests. Data will be analyzed at study completion.

Sample size was estimated a priori based on a two-tailed type I error of 0.05. For a difference of 1.5 points in HgbA1c and a power of 80%, 12 participants are required per intervention group. This number was increased by 30% to account for participant loss during screening, and an additional 30% to account for participant attrition, yielding 19 participants per intervention group (total 38 participants). An additional 12 participants have been enrolled using pilot funding from the University of Minnesota (of which 8 were eligible and 6 completed the entire study intervention).

This estimate uses preliminary data from existing LoBAG30 studies which were collected in a carefully controlled research setting. This differs from the conditions planned for this study. There are no data on the performance of the LoBAG30 diet in a free-living population of subjects with DM2. Thus, we will generate data that can be used to estimate effect size and variability for a power calculation for a future larger clinical trial.

With a goal of 38 plus 6 subjects completing the entire 12-week intervention, we anticipate recruiting up to 70 subjects in total.

If a subject withdraws from the study prior to study completion they will be invited to complete the final study visit prior to withdrawal, if possible. Any data collected from the subject prior to study withdrawal will be included in the final analysis. In the case of subject withdrawal an additional subject will be recruited to replace accordingly, dependent on funding.

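### Participants withdrawn for under 80% compliance have no secured week-12 HgbA1c, so the primary comparison can lose values, or take in early ones, because of behaviour after randomisation

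*Combined protocol and SAP*

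**What the plan says.** The withdrawal rule is in Section 4.8: "Subjects will be withdrawn from the study in the case of a significant adverse event, consent withdrawal, or failure of the subject to adhere". A threshold is then attached to the last of these grounds: "Failure to adhere to the protocol will be defined as compliance with <80% of requested study activities".

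The endpoint is in Section 4.7: "The primary outcome will be HgbA1c at the end of the 12-week study period". The arms are compared by an unpaired t-test. Section 4.3 places the final visit at the end of week 12.

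Section 4.7 also deals with people who leave early:
- Those who leave before the end are offered one last assessment: "they will be invited to complete the final study visit prior to withdrawal, if possible".
- Values already in hand are kept: "Any data collected from the subject prior to study withdrawal will be included in the final analysis".
- The numbers are made up where money permits: "In the case of subject withdrawal an additional subject will be recruited to replace accordingly, dependent on funding".

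Appendices 1 and 2 both list an HgbA1c draw at Visit 4 (week 6). Section 4.3 says midpoint blood is stored and analysed later if funding permits, and no analysis use of a week-6 HgbA1c is given. Neither appendix has an assessment after withdrawal. The plan names no analysis set and no method for missing HgbA1c.

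**The concern.** Compliance is observed only after randomisation and may be related both to the assigned diet and to glycaemic control. If low compliers leave without a week-12 measurement, the participants compared at week 12 are a selected part of those randomised. If the loss and its relation to HgbA1c differ by arm, the comparison is no longer protected by randomisation. Replacing withdrawn subjects restores the count but not the randomised comparison.

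This matters for the trial's purpose. The Project Summary and Section 1.3 aim at a free-living population, and Section 4.7 says the results will supply effect size and variability for a larger trial, so a distortion would carry forward. Analysis wording can be mended later; a week-12 value that was not collected cannot be recovered.

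**Working it through.** **1. What each safeguard supplies at week 12**

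| Safeguard | Source | What it leaves open |
|---|---|---|
| Invitation to the final visit | 4.7 | Optional, and timed before withdrawal, so possibly well before week 12 |
| Inclusion of collected data | 4.7 | Cannot supply a value never measured; no rule on whether an early value counts as week 12 |
| Week-6 HgbA1c | Appendices 1 and 2 | Not a week-12 value; analysis depends on funding (4.3) |
| Replacement | 4.7 | Restores numbers only; depends on funding |

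**2. Is an early value equivalent?** Section 1.1 reports, for 8 men on LoBAG30, mean glycated hemoglobin of 10.0% at baseline, 8.7% at 5 weeks and 7.5% at 10 weeks.
- Fall by 5 weeks: 10.0 - 8.7 = 1.3 points.
- Fall by 10 weeks: 10.0 - 7.5 = 2.5 points.
- Ratio: 1.3/2.5 = 52%.

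In that setting about half of the 10-week fall had appeared by 5 weeks. An exit value is not a week-12 value.

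**3. Size of a possible bias.** The plan gives no figure for losses under the 80% rule, so there is nothing of its own to reproduce. The loss shares and gaps below are assumptions.

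In each arm, let p be the share without a week-12 value and g the mean week-12 HgbA1c of those lost minus that of those retained. Then:

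- all-randomised mean = retained mean + p × g
- shift in the LoBAG-minus-control difference = -(pT × gT - pC × gC), with T for LoBAG and C for control

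With the same g in both arms this becomes -(pT - pC) × g:

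| Loss, LoBAG v control | g = 0.5 | g = 1.0 | g = 1.5 |
|---|---|---|---|
| 15% v 15% | 0 | 0 | 0 |
| 20% v 15% | -0.025 | -0.050 | -0.075 |
| 30% v 15% | -0.075 | -0.150 | -0.225 |

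A negative shift favours LoBAG; reversing the arms reverses the sign. Against the 1.5-point design difference, 0.075/1.5 = 5% and 0.225/1.5 = 15%.

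**4. Equal loss is not enough.** Suppose both arms lose the same share, but loss is related to outcome in the LoBAG arm only (gC = 0). The shift is then -p × gT. At p = 25% it is -0.125, -0.25 and -0.375 for gT = 0.5, 1.0 and 1.5. A simulation of 20,000 runs took 22 randomised per arm (half of the 44 in Section 4.1), an assumed SD of 1.27 and no true difference as randomised. It gave shifts of about -0.13, -0.25 and -0.37, and two-sided type I error of 6.0%, 8.4% and 12.7%. With no gap it gave 5.2%. The documents state no SD; by the normal approximation, values of about 1.26 to 1.31 reproduce the plan's 12 per group.

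**The case against.** The strongest reply is that the plan already looks after early leavers. It invites them to a final visit and promises to analyse what was collected, which points away from a completers-only analysis. The illustrations above treat everyone lost as contributing no value, that is, as if the invitation always failed. They are also modest against sampling error: with 22 per arm and SD 1.27 the standard error of the difference is 1.27 × √(2/22) = 0.38, so 0.075-0.225 is about 0.2-0.6 of it. This stands as a limit on the size. It does not close the gap, because the invitation is optional and not tied to week 12.

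A reader might infer more than the documents support:
- **That the invitation excludes participants withdrawn by the investigator.** Section 4.8 lists consent withdrawal among the grounds for being withdrawn, and 4.7 goes on to speak of subject withdrawal generally. The natural reading covers both.
- **That the urine marker makes withdrawal unequal by arm.** Section 4.4 describes nitrogen/creatinine as a marker for the LoBAG30 diet. However, urine, surveys and food diaries are collected without restriction by arm, no cut-off is given, and nothing says that diet intake counts toward the 80%.
- **That Section 4.9 predicts many withdrawals under the rule.** It expects lower compliance with the diets, not with study activities. The pilot figure in 4.7 (6 of 8 eligible completed) covers all causes, with no reasons given.
- **That the stopping rule adds to the bias.** It reads "The study will be stopped if >50% of subjects cannot meet compliance with >80% of study activities". It differs from the withdrawal rule only at exactly 80%, which is an editorial point.

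**Conclusion.** The concern holds as a preventable risk to the primary comparison, and it should be fixed. The firm part rests on the text alone: withdrawal below 80% is mandatory, no passage secures a week-12 HgbA1c afterwards, and the plan does not say how early or missing values enter the t-test.

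The size is not established. It would be wrong to infer that the result will be biased, or biased towards LoBAG. The bias is zero if loss shares and outcome gaps match across arms, and its sign depends on which arm loses more and on how those lost differ. The range of about 0.08-0.23 points rests on assumed loss of 30% v 15% and an assumed gap of 0.5-1.5 points, the same in both arms.

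**What to change.** 1. **Section 4.8.** State that compliance below 80% does not end outcome collection. Seek the scheduled week-12 HgbA1c from every randomised participant who has not withdrawn consent. Leave the safety and consent grounds unchanged.
2. **Section 4.7, comparison.** Make the primary comparison all randomised participants by assigned arm, regardless of compliance, and count replacements as additional participants.
3. **Section 4.7, timing and missing values.** Pre-specify one week-12 window. Enter early-exit HgbA1c, and week-6 HgbA1c if assayed, at their actual times and not as week-12 values, for example in a likelihood-based repeated-measures model that includes baseline. Such a model assumes that missingness is explained by the observed data. Add a sensitivity analysis that shifts the assumed week-12 values of those missing, separately by arm. Report the set with at least 80% compliance only as a sensitivity analysis.
4. **Minor.** State which activities count toward the 80%. For example, Appendix 1 lets the Visit 3 weight and urine collection be missed when the dietitian consult is by phone, and Appendix 2 cancels in-person visits for COVID-19 exposure or symptoms. Whether these count is not said.

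The cost is protocol and analysis wording, plus one blood draw of an already scheduled type per affected consenting participant (number unknown). The estimated effect may be smaller than among compliant participants.

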#### **4.9. Anticipated Problems and Proposed Solutions**

Although a free-living study cohort was purposefully chosen to answer the central question of this study, it is anticipated that compliance with study diets in this cohort will be lower than that in previous LoBAG diet studies. To address this, measures of compliance have been included, and frequent phone calls added to the protocol to encourage diet compliance. Although the dietary interventions in this study are meant to be weight stable, we acknowledge that weight change during the study may influence our results. For this reason, we have included three predetermined points in the protocol when caloric advice can be adjusted if indicated. Finally, use of medications for diabetes could impact the size of the effect of the LoBAG30 diet on HgbA1c, and so we have limited inclusion criteria to no glycemic medication or metformin only. We will also use stratified randomization to ensure equal distribution of medication use across study groups.

#### **5.0 Retention of Study Records**

Study records and data will be retained following completion of the study, in compliance with NIH and University of Minnesota requirements. Signed and dated HIPAA authorizations and consent documents will be maintained for at least 6 years after completion of the research. Other study records will be maintained for at least 3 years after completion of the research.

## Appendix 1: Timeline and Details of Study Visits

**Screen.** No visit needed. Will usually be done by telephone; may also be done by email or in person. (20 minutes)

**Visit 1.** Consent and Screening Visit. (1 hour)

- Review consent document and obtain informed consent.
- Collect baseline compliance survey, Diet Satisfaction Questionnaire, and Diabetes Treatment Satisfaction Questionnaire. Can alternatively be collected at visit 2.
- Measure weight and height.
- Non-fasting blood draw (for HgbA1c, basic metabolic panel, and complete blood count)
- Collect urine sample (for baseline urine nitrogen and urine creatinine, urine microalbumin, and pregnancy test if female and premenopausal).
- Send home with 3-day food intake diary (to be used by the study dietitian for caloric planning; the same food diary will also be collected at visit 4 and visit 6).
- If funding allows, place Abbott Freestyle Libre CGM. Provide supplies to return the CGM sensor (by mail or in person).
- Provide stool collection kit. Give instruction in stool sample collection.

Details for stool sample collection:

- Subject self-collects at home by sampling a stool with a sterile swab and putting the sample in a collection tube containing a preservative.
- This room-temperature-stable sample can be delivered to study investigators by the subject at study visits, or can be returned through the mail.
- Study staff will put the de-identified sample into the CTSI storage freezer.

**Randomization.** No visit needed.

**NCC Diet Recall**

- If funding allows, telephone call conducted by the Nutrition Coordinating Center (NCC) for an unannounced 24 hour diet recall (30 minutes; prior to visit 2/diet start).

**Visit 2.** Diet Instruction and Baseline Labs. (5 hours; beginning of Week 1)

- Subjects bring in stool sample or return by mail.
- If applicable, subjects bring in CGM sensor or return by mail.
- Collect weight, height, blood pressure.
- Fasting blood draw (for plasma glucose, serum insulin, lipid panel, fructosamine, and a stored sample).
- Provide a test meal consistent with the assigned diet (Control diet arm: 50% carbohydrate, 15% protein, 35% fat or LoBAG30 diet arm: 30% carbohydrate, 30% protein, 40% fat). The composition of the control diet was chosen to be consistent with typical macronutrient intake in the United States (21) and consistent with ADA guidelines (1). In addition to the fasting samples, obtain plasma glucose and serum insulin at +30, +60, +90, +120, +180 and +240 minutes following the start of the meal.
- Collect 3-day food diary.
- Collect list of current medications.
- Collect baseline compliance survey, Diet Satisfaction Questionnaire, and Diabetes Treatment Satisfaction Questionnaire if not already administered at Visit 1.
- Meeting with study dietitian for diet instruction. Sample menus and recipes consistent with the assigned diet will be provided. Dietitian consult may be conducted by phone if needed to facilitate scheduling.
- If funding allows, provide Actigraph Activity Monitor for subject to wear between Visits 2 and Visit 3.

**Visit 3.** Diet Reinforcement. (1 hour; Week 2)

- If applicable, subjects return Actigraph Activity Monitor.
- Measure weight.

- Collect urine sample for urine nitrogen and urine creatinine.
- Meeting with study dietitian for reinforcement of diet advice. Adjust caloric intake if needed for goal of weight stability. Dietitian consult may be conducted by phone. If dietitian consult is conducted by phone the participant will be encouraged, but not required, to come to the study center for weight and urine sample collection (this exception applies to visit 3 only).

**Visit 3.1.** (5-10 minutes; Week 4)

- Telephone call conducted by study investigator or coordinator to encourage study compliance.

**Visit 4.** Midpoint Visit. (1 hour; Week 6)

- Subjects bring in stool sample or return by mail.
- Measure weight and blood pressure.
- Fasting or non-fasting blood draw for HgbA1c, fructosamine, and a stored sample.
- Collect urine sample for urine nitrogen and urine creatinine.
- Meeting with study dietitian for reinforcement of diet advice. Adjust caloric intake if needed for goal of weight stability. Dietitian consult may be conducted by phone.
- Collect 3-day food diary.
- Collect list of current medications.
- Collect compliance survey and Diabetes Treatment Satisfaction Questionnaire

**Visit 4.1.** (5-10 minutes; Week 8)

- Telephone call conducted by study investigator or coordinator to encourage study compliance.

**Visit 5.** Diet Reinforcement. (1 hour, week 9-10)

- Measure weight.
- Collect urine sample for urine nitrogen and urine creatinine.
- Meeting with study dietitian for reinforcement of diet advice. Adjust caloric intake if needed for goal of weight stability. Dietitian consult may be conducted by phone.
- If funding allows, place Abbott Freestyle Libre CGM. Provide supplies to return the CGM sensor (by mail or in person).
- If funding allows, provide Actigraph Activity Monitor for subject to wear between Visits 5 and Visit 6.

**Visit 5.1.** (5-10 minutes; Week 11)

- Telephone call conducted by study investigator or coordinator to encourage study compliance.

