### 4.1. Study cohort

Up to 70 men and women with DM2 will be recruited and enrolled (dependent on funding), for a goal of 44 participants completing the trial.

To be eligible, subjects must be  $\geq 18$  years of age, have a previous diagnosis of DM2 by ADA criteria (20) and have a HgbA1c of 7.0-9.5% while either taking no medications for diabetes or using metformin alone.

Exclusion criteria will be:

- 1) type 1 diabetes mellitus,
- 2) treatment with insulin,
- 3) BMI <25 kg/m^2,
- 4) lack of weight stability defined as a change in weight of more than 5 pounds in the prior 3 months,
- 5) estimated glomerular filtration rate < 60 ml/minute/1.73 m^2,
- 6) urine albumin >300 mg/g creatinine,
- 7) pregnancy or immediate plans to become pregnant,
- 8) breast feeding,
- 9) dietary restriction(s) that would preclude consumption of study diets,
- 10) inability or unwillingness to prepare meals,
- 11) anemia, which would affect interpretation of HgbA1c,
- 12) presence of any disease which would make adherence to the study protocol difficult, and
- 13) use of antibiotics in the 3-month period prior to enrollment.

Subjects will be recruited from the University of Minnesota and surrounding communities. In addition, potential subjects will be identified from the Fairview patient population using Informatics Consulting Services (ICS) through the CTSI, and mailed letters informing them of possible study eligibility by the Fairview Research Administration.

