#### **4.3. Intervention**

A randomized, controlled, parallel group design will be used to compare the effects of the LoBAG30 diet or a balanced diet consistent with current ADA guidelines on our outcomes. Dietary intervention periods will be 12 weeks long. Both the LoBAG and control diets will consist of common foods.

Subjects will be asked to keep their physical activity level constant during the study. Medications for diabetes will be continued without change during the study. Medications will be monitored, and if a participant's medications are altered this will be noted. If antibiotics are used during the study this will be recorded. Subjects will be instructed that they do not need to monitor blood sugars regularly at home.

After enrollment and consent subjects will be randomized in a 1:1 allocation ratio to the LoBAG30 diet or a balanced diet consistent with ADA guidelines. Randomization will be stratified by diabetes treatment at enrollment (no glycemic medications or metformin) and by HgbA1c (7.0-8.5% or 8.5-9.5%), and implemented within stratum using randomly permuted block sizes of 2 and 4. If closely related subjects choose to enroll together (for example spouses or subjects that live together, and would typically share meals) they will be randomized to the same study arm. Baseline measures will be collected. Subjects will meet individually with the study dietitian, who will provide diet instruction, sample menus, and recipes consistent with the assigned diet. Dietitian consultation may be conducted

in person or by phone. During week 2 subjects will have a repeat consult with the dietitian to reinforce diet instruction. If weight has changed caloric intake will be adjusted as necessary for a goal of weight stability. A midpoint visit will be conducted at week 6, during which subjects will provide a blood sample, urine sample, and a stool sample, and will consult with the dietitian for reinforcement of diet advice. If weight has changed caloric intake will be adjusted to prevent further change. Midpoint blood and stool samples will be stored and analyzed in the future based on available funding. At week 9 subjects will consult with the study dietitian for reinforcement of diet advice and collection of a urine sample to assess compliance. The final study visit will be at the end of week 12. All outcome measures will be assessed at the final visit.

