If funding is available continuous glucose monitoring (CGM) will be added at the beginning and end of the study intervention. Subjects will be asked to wear the Freestyle Libre Pro CGM system for 2 weeks following the screening visit (visit 1) and for 2 weeks between visit 5 and visit 6. The CGM sensor will be worn on the back of the arm and will monitor and record interstitial glucose continuously throughout periods of CGM use. Subjects will be blinded to CGM glucose data. Sensors will be returned to study staff by mail or in person at study visits. Subjects will be given the option to receive a copy of CGM data, and to review this data with study staff, at the final study visit.

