#### **4.5. Subject Compensation**

Subjects will be provided a total stipend of \$600 for completion of the study. This amount includes a weekly stipend to partially account for the increased price of required foods (\$15 per week), compensation for time (average \$15 per week), and a bonus for study completion (\$240). Payments will be made at regular intervals during the study. If a subject withdraws from the study before completion, compensation will be provided for each week of participation up to the time of withdrawal. In addition to the above compensation, parking will be paid for at study visits.

Subjects who come for a screening visit only (do not qualify to go forward with the study) will be mailed a check with compensation (\$30). Subjects who enroll in the study will be given the option of payment using pre-paid debit cards with the Greenphire ClinCard system. If a subject chooses this option, they will be given a handout with instruction on use of the card. If a subject prefers not to use this option, they will be paid through checks mailed following study visits. The payment schedule will be the same with either reimbursement option, except that check processing may delay reimbursement by a few weeks.

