**NCC Diet Recall**

- If funding allows, telephone call conducted by the Nutrition Coordinating Center (NCC) for an unannounced 24 hour diet recall (30 minutes; Week 9-12).

**Visit 6.** Final Visit (5 hours; end of Week 12)

- Subjects bring in stool sample or return by mail.
- If applicable, subjects return Actigraph Activity Monitor.
- If applicable, subjects bring in CGM sensor or return by mail.
- Collect weight and blood pressure.
- Collect urine sample for urine nitrogen and urine creatinine.
- Fasting blood draw (for HgbA1c, plasma glucose, serum insulin, lipid panel, fructosamine, and a stored sample).
- Provide a test meal consistent with the assigned diet (Control diet arm: 50% carbohydrate, 15% protein, 35% fat or LoBAG30 diet arm: 30% carbohydrate, 30% protein, 40% fat). In addition to the fasting samples, obtain plasma glucose and serum insulin at +30, +60, +90, +120, +180 and +240 minutes following the start of the meal.
- Collect 3-day food diary.

- Collect list of current medications.
- Collect end of study compliance survey, Diet Satisfaction Questionnaire, and Diabetes Treatment Satisfaction Questionnaire.
- Meeting with study dietitian for debriefing and dietary advice for after study completion. Dietitian consult may be conducted by phone.

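### HgbA1c, the primary endpoint, has no start-of-diet value: its only pre-diet reading is the screening value, so the within-arm pre/post change carries a small selection shift of unknown direction

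*Combined protocol and SAP*

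**What the plan says.** **Schedule.** Appendix 1 draws HgbA1c at Visit 1 ("Non-fasting blood draw (for HgbA1c, basic metabolic panel, and complete blood count"), at Visit 4 in week 6, and at Visit 6 ("Fasting blood draw (for HgbA1c, plasma glucose, serum insulin, lipid panel, fructosamine, and a stored sample"). The Visit 2 list, taken as the diet starts, is "Fasting blood draw (for plasma glucose, serum insulin, lipid panel, fructosamine, and a stored sample", with no HgbA1c. Appendix 2 gives the same Visit 2 list.

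**Use of the Visit 1 value.** Section 4.1 requires that subjects "have a HgbA1c of 7.0-9.5% while either taking no medications for diabetes or using metformin alone". Section 4.5 provides for "Subjects who come for a screening visit only (do not qualify to go forward with the study", so people can fail at that visit. Section 4.3 stratifies randomization by treatment "and by HgbA1c (7.0-8.5% or 8.5-9.5"), and both appendices place randomization between Visits 1 and 2.

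**Interval.** No maximum gap between Visit 1 and Visit 2 is given. The only cue is CGM wear "for 2 weeks following the screening visit (visit 1"). CGM depends on funding in section 4.3 and Appendix 1, whereas Appendix 2 lists sensor placement at Visit 1 without that condition.

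**Analysis.** Section 4.7 states: "Results will be compared pre and post diet intervention (within an individual subject") by paired t-tests, and between diets by unpaired t-tests. It does not say which HgbA1c is the pre value. Aim 1 (section 3.1) is framed as a reduction over 12 weeks.

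**The concern.** Glucose, insulin, lipids and fructosamine each have a value at the start of the diet. The primary endpoint does not. Two things follow for its within-person change.

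First, the pre reading had to fall inside a window for the person to enter. On re-measurement, readings that were in the window partly by chance move back towards the source-population mean, with no diet effect at all.

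Second, the reading predates the diet by an interval that the plan does not limit. Any change in HgbA1c over that interval is counted as change on the diet.

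What is at stake is the paired tests, the reported within-arm changes, and any within-arm change or variability carried from this study into planning the later trial that section 4.7 mentions. Unless HgbA1c is measured at Visit 2, neither component can be assessed afterwards.

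**Working it through.** **1. Visit lists side by side**

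| Visit | HgbA1c | Fructosamine | Fasting glucose, insulin, lipids |
|---|---|---|---|
| 1, screening | yes | no | no |
| 2, start of diet | no | yes | yes |
| 4, week 6 | yes | yes | no |
| 6, end of week 12 | yes | yes | yes |

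There is exactly one pre-diet HgbA1c, in either appendix. If CGM is worn for its 2 weeks before Visit 2, Visit 1 to Visit 6 spans at least 2 + 12 = 14 weeks.

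**2. The plan's own figures.** The plan gives no figure for selection or drift. Its 12 per group for a 1.5-point difference does not depend on this point. The 1.5 points serve below only as a yardstick.

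**3. Size of the selection shift.** Assumed inputs, none of them in the documents: source mean μ of 7.0-9.0%, between-person SD σ_T of 1.0-1.3, within-person SD σ_w of 0.2-0.5, normal distributions, no true change. The window of 7.0-9.5% is from section 4.1. Write σ² = σ_T² + σ_w², a = (7.0 − μ)/σ and b = (9.5 − μ)/σ. The expected second reading minus the first, given that the first is in the window, is

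shift = −(σ_w²/σ) × [φ(a) − φ(b)] / [Φ(b) − Φ(a)].

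- μ = 7.0, σ_T = 1.0, σ_w = 0.5: σ = 1.118, a = 0, b = 2.236. Ratio = (0.3989 − 0.0327)/(0.9873 − 0.5000) = 0.751. Shift = −0.2236 × 0.751 = **−0.168**.
- μ = 7.5, σ_T = 1.0, σ_w = 0.35: σ = 1.0595, a = −0.472, b = 1.888. Ratio = (0.3569 − 0.0672)/(0.9705 − 0.3185) = 0.444. Shift = −0.1156 × 0.444 = **−0.051**.
- μ = 8.25, the midpoint of the window: a = −b, so the shift is **0**.
- μ = 9.0, σ_T = 1.0, σ_w = 0.5: a = −1.789, b = 0.447. Ratio = (0.0805 − 0.3610)/(0.6726 − 0.0368) = −0.441. Shift = **+0.099**.

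These two ends, about −0.17 and +0.10, bound the whole grid. If the within-person error is instead taken as a CV of 2-6%, simulation gives −0.12 to +0.13.

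**4. Effect on a paired t-test in one arm.** n = 22 (44 completers over two arms); the SD of change is assumed to be 0.6-0.8. Non-centrality = shift × √22 / SD, two-sided 5%.

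- Shift 0.05: 0.391 (SD 0.6) gives 6.6%; 0.293 (SD 0.8) gives 5.9%.
- Shift 0.168, SD 0.8: 0.985 gives 15.6%. SD 0.6 is not paired with this shift, because σ_w = 0.5 alone makes the SD of change about √2 × 0.5 = 0.7.

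**5. Between-arm comparison.** Selection precedes randomization and acts alike on both arms. In simulation with no diet effect, the unpaired t-test stayed at about 5% on final values and on change.

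**6. What a second pre-diet reading adds to an adjusted comparison.** With an assumed SD of 0.6 for individual true change (τ) and σ_T = 1.0, the residual variance of week-12 HgbA1c is σ_w² + τ² + σ_T²σ_w²/(σ_T² + σ_w²) given one reading. Given two, the last denominator becomes 2σ_T² + σ_w².

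- σ_w = 0.2: 0.438 against 0.420, a reduction of about 4%.
- σ_w = 0.5: 0.810 against 0.721, a reduction of about 11%.

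**The case against.** The strongest reply is that the hypothesis is between-arm, the primary endpoint is HgbA1c at week 12, and section 4.7 compares diets by an unpaired t-test without baseline adjustment. Randomization balances the selection. This stands: the point concerns the within-arm results and precision, not the validity of the main comparison.

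A reader might go further than the documents allow in four ways.

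- *The selection shift is a spurious fall.* The window is bounded on both sides and the source mean is not given. The shift is downward below a source mean of 8.25%, zero at it, and upward above it.
- *The paired test is badly inflated, say to 13-20%.* Those rates follow from a total shift of 0.15 (SD of change 0.8 and 0.6). Selection alone gets that far only in the most extreme corner of the grid. From a shift of 0.05, the other 0.10 would be drift whose size and direction are assumed. It is a scenario, not an estimate.
- *The gap is unlimited.* No maximum is written, but nothing describes or invites long gaps. Weight stability over the prior 3 months and unchanged diabetes medication during the study both restrain drift. Section 3.2 also notes that HgbA1c equilibrates more slowly than fructosamine.
- *Visit 1 is stated to be the eligibility reading.* No sentence says so. It is inferred from the visit's purpose, its HgbA1c draw and the stipend rule for those who do not qualify.

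It is also fair that a Visit 2 value comes after randomization, and the plan does not say when participants learn their arm. It is still a pre-diet value: the fasting draw precedes the test meal, and diet instruction belongs to the same visit or later.

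**Conclusion.** The point holds as a low-cost improvement. The omission of HgbA1c from the baseline draw is plain in both appendices, and section 4.7 never names the pre value. The within-arm change in the primary endpoint is therefore selected on the entry window and does not start at week 0.

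The likely consequence is small. The selection shift of about −0.17 to +0.10 points compares with a planning difference of 1.5, so even the larger end is about a ninth of it (0.168/1.5 = 11%). The direction depends on who is screened. A shift of 0.05 takes a nominal 5% paired test to about 6-7%; the 15.6% above belongs to the extreme corner of the inputs. All of this rests on assumed source mean, between-person SD, within-person SD and SD of change. Drift before the diet would add to the shift or offset it, and the documents do not allow it to be sized.

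The documents do not support a claim that the between-arm comparison of week-12 HgbA1c is biased.

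**What to change.** 1. Add HgbA1c to the Visit 2 fasting draw in Appendix 1 and Appendix 2.
2. In section 4.7, define the Visit 2 value as pre for the within-arm paired analysis. Keep the Visit 1 value for eligibility and stratification.
3. If the between-arm comparison is baseline-adjusted, both pre-diet readings may enter as covariates. Selection is balanced by randomization there, and the second reading adds precision.
4. For participants already past Visit 2, assay the stored Visit 2 sample if its type allows, which the plan does not say. Otherwise use the Visit 1 value, flag it, and report the Visit 1 to Visit 2 interval.
5. Label the within-arm tests as descriptive.

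If the assay cannot be added, the minimum is to name the Visit 1 value as baseline and state a maximum Visit 1 to Visit 2 interval.

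The cost is one HgbA1c assay per participant on blood already being drawn, about 44 to 70 assays given the completion goal and enrolment ceiling in section 4.1, plus wording changes. No visit or venepuncture is added. The drawback is mixed baselines for those already enrolled, including the pilot-funded participants in section 4.7 (8 eligible, 6 completed), which is why the flag and the interval should be reported.
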